**TO BE COMPLETED ON DAY OF DOSING:**

- Vital sign measurements: systolic / diastolic blood pressure (BP), pulse rate, respiratory rate and temperature

**5.3.2 Evaluation schedule B*****Pre-Dose***

- Adverse events and DLTs since the previous assessment
- New or changes to existing medications
- Physical examination of major body systems
- Vital sign measurements: systolic / diastolic blood pressure (BP), pulse rate, respiratory rate and temperature
- Weight
- ECOG performance status

It is recommended that subjects also receive antipyretic prophylaxis, steroid prophylaxis and hydration at the time of each injection of enadenotucirev (See section 8.3). The recommended regime is:

- 1 hour prior to administration
  - IV hydrocortisone 100mg
  - PO Paracetamol 1000mg

**5.4 Post dose evaluations**

Once the enadenotucirev has been administered to the patient the following post dose evaluations should be carried out:

- Vital sign measurements (systolic / diastolic blood pressure (BP), pulse rate, respiratory rate and temperature):

**First Dose:**

After the first dose of enadenotucirev the patient's vital signs must be monitored at the following time points:

- Immediately after the end of the infusion
- 30 minutes ( $\pm 5$  minutes) post end of infusion
- 1 hour ( $\pm 15$  minutes) post end of infusion
- 4 hour ( $\pm 15$  minutes) post end of infusion
- 6 hour ( $\pm 15$  minutes) post end of infusion

**Subsequent doses:**

On all subsequent doses the patient's vital signs must be monitored at the following time points:

- Immediately after the end of the infusion
- 30 minutes ( $\pm 5$  minutes) post end of infusion
- 1 hour ( $\pm 15$  minutes) post end of infusion
- 3 hour ( $\pm 15$  minutes) post end of infusion

They will also receive a further dose of Hydrocortisone (IV) and paracetamol (PO) at 3 hours [See section 8.3]. If they are clinically well and vital signs are normal they can be discharged. If not improving consider admission for further active management.

## 5.5 Weeks 1/2

The following assessments should be completed for all patients:

### Dosing day 1:

- Pre dose – Evaluation Schedule A (5.3.1)
- Post dose evaluations (5.4)

### Dosing day 2:

- Pre dose – Evaluation Schedule B (5.3.2)
- Post dose evaluations (5.4)

### Dosing day 3:

- Pre dose – Evaluation Schedule A (5.3.1)
- Post dose evaluations (5.4)

### **Faecal sample (after last dose of enadenotucirev):**

Home collection and postage of faecal sample & diet questionnaire (optional consent required and may not be applicable to all participating sites)

## 5.6 Week 3

### **5.6.1 Dosing Groups 1, 2 & 3**

Day 1 – Evaluation Schedule A (5.3.1)

### **5.6.2 Dosing group 4**

### Dosing day 1 & 5:

- Pre dose – Evaluation Schedule A (5.3.1)
- Post dose evaluations (5.4)

## 5.7 Week 4, 5, 6, 7

### **5.7.1 Week 4 only**

The following assessments should be completed for **all patients**, during week 4 only and in addition to the assessments in 5.7.2.

### Tumour biopsy

During week 4 (second week of chemoradiation) a biopsy of the tumour is mandated as part of the trial. This should be performed at endoscopy by an experienced endoscopist. Under direct visualisation (proctoscopy) a maximum of 3 samples of tissue will be taken, each measuring less than 6mm.

### Investigational blood sample

An investigational blood sample will also be taken on day 10 of chemoradiation. (See Laboratory manual)

### Faecal sample (after week 4 treatment):

Home collection and postage of faecal sample & diet questionnaire (optional consent required and may not be applicable to all participating sites)

### **5.7.1 Week 4, 5, 6, 7 - Other assessments**

To be completed, for **all patients**, as standard of care prior to chemoradiation:

- Evaluation Schedule A (5.3.1)

### 5.7.2 Week 7 only

#### **Faecal sample (after week 7 treatment):**

Home collection and postage of faecal sample & diet questionnaire (optional consent required and may not be applicable to all participating sites)

## 5.8 Week 8, 9

### 5.8.1 Dosing group 1

Day 1 Evaluation Schedule A (5.3.1)

### 5.8.2 Dosing groups 2, 3 & 4

#### **Dosing day 1:**

- Pre dose – Evaluation Schedule A (5.3.1)
- Post dose evaluations (5.4)

#### **Dosing day 2:**

- Pre dose – Evaluation Schedule B (5.3.2)
- Post dose evaluations (5.4)

#### **Dosing day 3:**

- Pre dose – Evaluation Schedule A (5.3.1)
- Post dose evaluations (5.4)

## 5.9 End of trial evaluations at 13 weeks (+/- 3 days)

The following assessments should be completed for **all patients**:

- Adverse events and DLTs since the previous assessment
- New or changes to existing medications
- Physical examination of major body systems
- Vital sign measurements: systolic / diastolic blood pressure (BP), pulse rate, respiratory rate and temperature
- Weight
- ECOG performance status
- Local laboratory assessments:
  - Urine dipstick
  - Blood samples for laboratory safety tests:
    - Haematology – Hb, white blood cells (WBC) with differential count (neutrophils and lymphocytes) and platelets
    - Biochemistry – sodium, potassium, calcium, phosphate, urea, creatinine, total protein, albumin, bilirubin, alkaline phosphatase (alk phos), AST and/or ALT and LDH
    - Coagulation screen (aPTT and INR)

#### **MRI:**

Patients should also have their standard of care, post treatment MRI scan to assess for response. Can be up to +/- 7 days of week 13.

#### **Investigational blood sample**

An investigational blood sample will also be taken during week 13, at the same time as the other blood tests.

#### **Faecal sample:**

Home collection and postage of faecal sample & diet questionnaire (optional consent required and may not be applicable to all participating sites)

## 5.10 Follow-up evaluations (post 14+ weeks)

The patient will return to follow-up as per standard care in the NHS, with surgery completed as per standard care at week 14+. A further visit to the trial team 4-6 weeks after surgery should occur to formally record the following:

1. Pathological resection specimen findings as per the RCPATH reporting guidelines recorded on CRF
2. Neoadjuvant rectal score details
3. Any surgical and other complications – AE assessments
4. ECOG performance status
5. Investigational Blood sample taken

If patient has not received surgery due to complete clinical response, they should be followed up as per standard of care. Confirmation of their complete clinical response will be obtained from their medical records if available.

## 6 EARLY PATIENT WITHDRAWAL

### Treatment Withdrawal

During the course of the trial, a patient may withdraw early from treatment. This may happen for a number of reasons, including:

- Unacceptable toxicity
- AE/SAEs requiring discontinuation
- Loss to follow-up
- Significant protocol deviation or inability to comply with trial procedures
- Clinical decision
- Patient decision

When the patient stops treatment early, the 'End of Treatment' Form needs to be completed, and any other relevant CRFs (e.g. SAE Form). The reason for and date of withdrawing from treatment early should be clearly documented in the medical records. The following evaluations should be carried out on early withdrawal unless the patient has withdrawn consent also.

- Physical examination of major body systems
- Adverse events and DLTs since the previous assessment
- Vital sign measurements: systolic / diastolic blood pressure (BP), pulse rate, respiratory rate and temperature
- ECOG performance status
- Local laboratory assessments:
  - Blood samples for laboratory safety tests:
    - Haematology – Hb, white blood cells (WBC) with differential count (neutrophils and lymphocytes) and platelets
    - Biochemistry – sodium, potassium, calcium, phosphate, urea, creatinine, total protein, albumin, bilirubin, alkaline phosphatase (alk phos), AST and/or ALT and LDH
    - Coagulation screen (aPTT and INR)

Patients who have stopped treatment early should continue to be followed-up for toxicity, response and survival, unless patient consent for follow-up is withdrawn.

### Consent Withdrawal

Consent withdrawal means that a patient has expressed a wish to withdraw from the trial altogether. Under these circumstances, the site needs to document all relevant discussions in the patient notes and notify the Trial Office, which will allow the office to mark all future CRFs as not applicable.

Under these conditions, investigators are still responsible to follow up any SAEs until resolution.

### Patient evaluability and replacement

All patients enrolled in the trial and who received at least one dose of enadenotucirev will be considered evaluable. Patients who are not evaluable will be replaced. The TMG may decide to replace a patient if they withdraw from the trial for a reason other than a DLT. The dose of a patient replacing a non-evaluable patient will be assigned in the same way as all other patients and they will not necessarily be allocated the same dose as the non-evaluable patient they replace.

Patients who do not complete the response primary endpoint evaluation will be treated as non-responders.

## 7 SAMPLES FOR LABORATORY ANALYSIS

### 7.1 Samples to be analysed in local Trust's laboratories

#### *Diagnostic Laboratories*

Samples for haematology, biochemistry and urinalysis will be labelled with standard patient identifiers and sent to the local hospital diagnostic laboratory. Results will be processed in the standard way and entered into the routine hospital reporting system. Samples will be stored, held, reported and subsequently destroyed in accordance with standard local laboratory practice.

#### *Pathology*

The routine diagnostic pathology samples and additional research samples taken at biopsies and during surgery will also be labelled, processed and reported according to local hospital protocols.

### 7.2 Samples to be sent to and analysed in a Central Laboratory

The following samples are required to be collected for shipment to central laboratories:

Time Point	Screening/Baseline	Week 1 / 2	Week 4	Week 7	Week 13	Week 14 +	4-6 weeks post-surgery
Investigational blood sample	X		X		X		X
Tumour sample for viral load and gene expression	X (archived diagnostic sample)		X (biopsy)			X (resection)	
Faecal sample (optional consent required – may not be applicable to all sites)	X	X	X	X	X		

Assay/sample handling and storage will be managed according to separate written instructions. The following sections summarise the arrangements for collection, close to patient handling, timings, and analytical laboratories responsible.

### 7.3 Labelling and confidentiality of samples sent

All samples sent to analytical Laboratories will be labelled with the trial patient number, sampling time-point and date/time taken. Should a laboratory receive any samples carrying unique patient identifiers the recipient must immediately obliterate this information and re-label as well as informing the trial office.

### 7.4 Clinical reporting of exploratory research assay results

Although the results of the CEDAR trial research assays are exploratory, and the assays performed are not to current NHS standards, clinically relevant genetic information could be revealed. Relevant results will be confirmed by an appropriate expert before the patient and their clinical care team are informed and changes may be made to their clinical care if required. Due to the exploratory nature of the assays and the subsequent results, patients will be given the option to decide if they would like to be informed of any clinically relevant genetic information via the consent form. The local site Principal Investigator will be notified by the appropriate expert if any clinically relevant genetic information is revealed. At this stage, patients will only be referred to by their unique trial number with it only being possible for the site team to re-identify the patient so that they can be contacted if required and if they provided consent.

### 7.5 Trial sample retention at end of trial

The Chief Investigator has overall responsibility for custodianship of the trial samples. Laboratories are instructed to retain any surplus samples pending instruction from the Chief Investigator on use, storage or destruction. It is possible that new or alternative assays may be of future scientific interest. At the end of the research trial any surplus samples may be retained for use in other projects that have received ethical approval. Hence, any surplus trial samples may be analysed as part of a separate ethically approved project, transferred to a licensed tissue bank where they will be managed in accordance with applicable host institution policies and the Human Tissue Act (HTA) requirements.

## 7.6 Withdrawal of consent for sample collection and/or retention

A patient may withdraw consent to provide samples for research at any time without giving a reason. The Investigator must ensure that their wishes are recorded in the medical record and will inform the Trial Office accordingly. The investigator should discuss with patients the valuable use of samples that have already been provided and under circumstances where these samples have already been processed and anonymised, it would not be possible to destroy such samples.

## 8 INVESTIGATIONAL MEDICINAL PRODUCTS (IMPS)

### 8.1 Name of IMPS

The trial is investigating the unlicensed drug enadenotucirev in combination with chemoradiotherapy. The chemotherapy agent used is capecitabine. Enadenotucirev and capecitabine are both considered IMPs.

### 8.2 Treatment dose and duration

#### Enadenotucirev

All participants will receive 3 x loading doses in weeks 1-2, prior to initiation of chemoradiotherapy. Loading doses should be given on 3 non-consecutive days over a 7-day period (e.g. Mon, Wed, Fri **or** Fri, Mon, Wed **or** other convenient schedule).

There are 2 different dosing patterns for the 3 loading doses.

- Low-Low-Low, for dosing groups 1 & 2; 3 individual doses of  $1 \times 10^{12}$ VP given
- Low-High-High, for dosing groups 3 & 4; 3 individual doses of (1)  $1 \times 10^{12}$ VP, (2)  $3 \times 10^{12}$ VP, (3)  $3 \times 10^{12}$ VP given

Further doses of enadenotucirev after the 3 loading doses are dependent on the dose schedule assigned, as per table below. See section 17.2 for information on dose decision making and allocation

Dose schedule	Loading x 3 (pre CRT) (3 doses given on 3 non-consecutive days over a 7 day period)	Concurrent		Maintenance x 3 (post CRT) (3 doses given on 3 non-consecutive days over a 7 day period)
		Week 1 Day 1 CRT (week 3 day 1)	Week 1 Day 5 CRT (week 3 day 5)	
1 (start level)	Low-Low-Low 1*			
2	Low-Low-Low 1*			Low-Low-Low 1*
3	Low-High-High 2*			Low-High-High 2*
4	Low-High-High 2*	$3 \times 10^{12}$ vp	$3 \times 10^{12}$ vp	Low-High-High 2*

 Low-Low-Low = 3 x doses at  $1 \times 10^{12}$ VP

 Low-High-High = 3 Doses, (1)  $1 \times 10^{12}$ VP, (2)  $3 \times 10^{12}$ VP, (3)  $3 \times 10^{12}$ VP

\* 3 doses administered on 3 non-consecutive days over 7 days

#### Dose Schedules 2 & 3:

After loading doses and completion of CRT, 3 x maintenance doses outlined in the table above of enadenotucirev will be delivered in weeks 8-9 for all participants assigned to dose schedules 2 & 3. Maintenance doses should be given on 3 non-consecutive days over a 7 day period. As with the loading doses, the maintenance doses are given in 2 different dosing patterns dependant on dosing schedule:

- Low-Low-Low, for dosing group 2; 3 individual doses of  $1 \times 10^{12}$ VP given
- Low-High-High, for dosing group 3; 3 individual doses of (1)  $1 \times 10^{12}$ VP, (2)  $3 \times 10^{12}$ VP, (3)  $3 \times 10^{12}$ VP given

#### Dose schedule 4:

After loading doses, participants assigned to dosing schedule 4 will receive enadenotucirev concurrently with CRT during their 1st week of CRT, as indicated in the table. This will consist of two doses delivered, one on the first and then last day of CRT in that week, post radiotherapy. Each dose will be given at  $3 \times 10^{12}$ VP

**NB Morning and evening doses of capecitabine are to be omitted on enadenotucirev dosing days.**

Participants will also receive 3 x maintenance doses of enadenotucirev delivered in weeks 8-9 after completion of CRT. Maintenance doses should be given on 3 non-consecutive days over a 7 day period and will be given as the Low-High-High dosing pattern consisting of 3 individual doses of (1) 1 x 10^12VP, (2) 3 x 10^12VP, (3) 3 x 10^12VP

### **Capecitabine**

Capecitabine must not be taken on enadenotucirev dosing days.

With the exception of enadenotucirev dosing days capecitabine should be taken twice daily (morning and evening) Monday to Friday for 5 weeks, concurrently with radiotherapy.

Capecitabine is taken daily at a dose of 900 mg/m^2 (the standard dose used for chemoradiotherapy treatment of locally advanced rectal cancer). Sites should use national dose banding tables for capecitabine.

CRT Week (trial week)		1 (trial week 3)					2 (trial week 4)					3 (trial week 5)					4 (trial week 6)					5 (trial week 7)					
Days		1-5					8-12					15-19					22-26					29-33					
Radiotherapy: 50 Gy/25#		#	#	#	#	#	#	#	#	#	#	#	#	#	#	#	#	#	#	#	#	#	#	#	#	#	#
Oral capecitabine* 900 mg/m  orally bd Mon – Fri x 5 weeks	Dose schedules 1, 2 & 3	X	X	X	X	X	X	X	X	X	X	X	X	X	X	X	X	X	X	X	X	X	X	X	X	X	X
	Dose schedule 4	X	X	X	X	X	X	X	X	X	X	X	X	X	X	X	X	X	X	X	X	X	X	X	X	X	X
		-	X	X	X	-	X	X	X	X	X	X	X	X	X	X	X	X	X	X	X	X	X	X	X	X	X
		-	X	X	X	-	X	X	X	X	X	X	X	X	X	X	X	X	X	X	X	X	X	X	X	X	X

### **8.3 Management of drug administration**

#### Enadenotucirev

Enadenotucirev is a live replicating oncolytic adenovirus; it is considered a BioSafety Level 1 (BSL-1) infectious substance. Appropriate precautions should be followed for a BSL-1 substance, as per section 8.4 and local site policy.

Subjects must receive antipyretic prophylaxis, steroid prophylaxis and hydration at the time of each injection of enadenotucirev. The recommended regime is:

- 1 hour prior to administration
  - IV hydrocortisone 100mg
  - PO Paracetamol 1000mg
- 3 hours following administration
  - IV hydrocortisone 100mg
  - PO Paracetamol 1000mg

It is also strongly recommended that all patients have loperamide prescribed prior to commencement of treatment, in case of development of diarrhoea (see section 9.3).

Patients should also be given a prescription for oral paracetamol 1000mg four times daily to be taken in the 24 hours after receiving enadenotucirev.

The enadenotucirev infusion solution should be made up as per the administration protocol. Once diluted in the infusion bag/syringe it must be administered to the patient within 6 hours of preparation. The diluted solution is stable at room temperature (20-26°C) for up to 1 hour. If not administered within 1 hour it can be stored at +2°C to 8°C for no longer than 6 hours until administration. The full infusion volume must be administered over a 15 minute (+/- 5minutes) period for all dosing groups.

**NOTE:** At the time of administration, the extension set used to administer enadenotucirev can be primed with saline. At the end of infusion, the line will also need to be flushed with saline. This will ensure that all 30 mL of diluted enadenotucirev are administered to the patient.

The patient should be observed after administration as per post-dosing assessments detailed in section 5.3. N.B. serious infusion reactions have been observed in previous trials of enadenotucirev, appearing to reflect cytokine responses to treatment. In the event of a serious infusion reaction the infusion should be discontinued and the patient monitored and treated as per standard local protocol for management of cytokine release syndrome. Further guidance on managing toxicities is given in section 9.2.

#### **Capecitabine**

Refer to the Summary of Product Characteristics (SPC) for full prescribing information and details of drug reconstitution, administration and stability (<http://www.medicines.org.uk/emc/>).

Patients will be instructed to take capecitabine tablets twice a day starting in the morning/evening, starting on the first day of radiotherapy. Tablets will be taken twice daily on every day that radiotherapy is given (therefore excluding the weekends). **Capecitabine must not be taken on enadenotucirev dosing days.**

It is recommended that patients are carefully monitored for ophthalmologic complications, such as keratitis and corneal disorders, especially if they have a prior history of eye disorders. Treatment of eye disorders should be initiated promptly. For patients with diabetes mellitus, caution must be exercised as it may be aggravated.

Patients should be instructed to take the drug twice daily as above **only** on the days radiotherapy is delivered. Doses should be omitted on enadenotucirev dosing days. Where the start of radiotherapy is delayed for scheduling reasons the start of concurrent chemotherapy should also be delayed.

Missed doses/dosing day will not be made up. The next dose must be taken as scheduled. Doses should NOT be doubled to make up for missed doses.

If a patient vomits after taking the tablets, they should not take another dose. The next doses should be taken as scheduled.

If a patient has taken their morning dose of capecitabine on an enadenotucirev dosing day, administration of enadenotucirev should be delayed to the next day of radiotherapy. Patients should be reminded to take their evening dose as normal and to not take capecitabine the following day. If delay of enadenotucirev dosing is not possible, enadenotucirev can still be administered and patients reminded to omit their evening capecitabine dose.

Any unused tablets should be returned to pharmacy (via research nurse). All patients are asked to keep a record of their capecitabine use in their site specific diary card. Diary cards will be reconciled by site staff and confirmation of capecitabine use to be recorded on the relevant CRF.

#### **8.4 Special precautions**

Enadenotucirev is a live replicating oncolytic adenovirus that has not been genetically modified, it is considered a BioSafety Level 1 (BSL-1) infectious substance. BSL-1 agents pose minimal potential hazard to personnel. Sites should follow local procedure for handling a BSL-1 biological agent, it is suggested that this includes:

- No eating and drinking in areas where enadenotucirev doses are prepared or administered
- Safe disposal of used vials and all equipment used to prepare and administer enadenotucirev

#### **8.5 Dose modification**

##### **Enadenotucirev**

No dose modifications may be made. **With the exception of renal injury, specifically proteinuria of 2+ where enadenotucirev must be delayed and or discontinued (see section 9.3),** treatment may be interrupted because of a non-DLT of Grade 3 or higher, at the discretion of the Investigator. Treatment may be resumed when all toxicities have returned to grade 2 or less, at the discretion of the Investigator. If two consecutive doses of enadenotucirev are missed due to enadenotucirev related toxicity, this constitutes a DLT, and no further enadenotucirev will be administered. If the subject misses a dose of enadenotucirev for any reason other than toxicity the dose should not be made up. The scheduling should continue as normal, from the next planned dose of enadenotucirev. If radiotherapy is

withheld for toxicity or other reasons, enadenotucirev should also be withheld and the dosing schedule should continue from the next planned dose once radiotherapy has resumed.

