#### **Low-High-High dosing regimen**

Since the cytokine release is believed to be the most important mediator of the adverse effects of viral therapy, this tolerising effect allows subsequent doses to be delivered with a lower risk of high grade side effects. Splitting the dose may therefore allow a higher and more effective dose without dose limiting toxicities.

After the first dose has been administered, the cytokine response to subsequent doses of enadenotucirev is attenuated when delivered within a few days of the first dose.

Attenuation of this cytokine response by administration of a well-tolerated day 1 dose of enadenotucirev to desensitise the cytokine response would allow the potential for delivery of higher subsequent doses to be tolerated. In turn this may allow more virus to be delivered to the tumour and increase the potential of clinical benefit. This type of dosing schedule is referred to as a “low-high-high” dosing regimen and has been successfully implemented in clinical studies of other systemically administered oncolytic viruses (Laurie et al, 2006).

Dosing groups 1 & 2 remain unchanged and will use a ‘low-low-low’ dosing regimen where all 3 doses pre and post chemoradiotherapy will be given at  $1 \times 10^{12}$ VP.

The low-high-high dosing regimen will be used for the pre and post chemoradiotherapy doses of enadenotucirev in dosing groups 3 & 4. The low dose is  $1 \times 10^{12}$ VP and the high dose is  $3 \times 10^{12}$ VP. All pre and post chemoradiotherapy doses will continue to be given on non-consecutive days, over a 7 day period.

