### 5.3 Pre-treatment evaluation

Evaluation schedule A applies to all patients prior to day 1 of any dose or sequence of treatment.

The table below summarises what pre dose evaluations (schedule A or B) should be undertaken for each patient on any given day, depending on which dosing group they are assigned to (Section 8.2 and 17.2 for more information). Loading and after loading doses of enadenotucirev should be given on 3 non-consecutive days over a 7-day period during weeks 1-2-and 8-9 (e.g. Mon, Wed, Fri **or** Fri, Mon, Wed **or** other convenient schedule). Doses given during the 1st week of chemoradiation should be given on day 1 and day 5. On each dosing day the following assessments are required:

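### Read literally, section 8.5 lets a schedule 3 or 4 patient who forfeits the Low dose of a Low-High-High course receive 3 × 10^12 vp next

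*Protocol*

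**What the plan says.** Section 8.5 of the protocol rules out any modification of the enadenotucirev dose. For a dose missed for a reason other than toxicity it says: "If the subject misses a dose of enadenotucirev for any reason other than toxicity the dose should not be made up". It then says: "The scheduling should continue as normal, from the next planned dose of enadenotucirev". After an interruption for toxicity, treatment may resume, but the section does not say at which step of a course.

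Section 1.2 explains the Low first dose: "the cytokine response to subsequent doses of enadenotucirev is attenuated when delivered within a few days of the first dose". It applies the pattern twice: "The low-high-high dosing regimen will be used for the pre and post chemoradiotherapy doses of enadenotucirev in dosing groups 3 & 4". Section 8.2 fixes the order in schedules 3 and 4 as 1, then 3, then 3 × 10^12 vp, and for schedule 4 says that the maintenance doses "will be given as the Low-High-High dosing pattern consisting of 3 individual doses of" these sizes.

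The dates are loose. Section 5.3 says: "Loading and after loading doses of enadenotucirev should be given on 3 non-consecutive days over a 7-day period during weeks 1-2-and 8-9". Section 8.2 repeats this for maintenance: "Maintenance doses should be given on 3 non-consecutive days over a 7 day period".

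**The concern.** The missed-dose rule is written for doses that are interchangeable. In a Low-High-High course they are not, because the first dose prepares the patient for the second. If the Low is forfeited, the next planned dose is a High, and the ban on dose modification stops a site from giving a Low in its place. The general rule can therefore remove a lead-in that the protocol chose to use before chemoradiotherapy and to repeat after it.

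What is at stake is patient safety at the level of the individual course. Section 1.2 names cytokine release as the main mediator of the adverse effects. Section 9.1 makes cytokine release syndrome of grade 3 or higher a dose-limiting toxicity (DLT), which ends trial treatment.

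**Working it through.** The plan gives no figure for this point. The check is a reading of the rules followed by calendar arithmetic.

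**Step 1: the rules side by side.** Section 8.2 makes the dose after the Low 3 × 10^12 vp. Section 8.5 skips a missed dose, goes to the next planned one and bars a change of size. No rule in protocol sections 5, 8 or 9 or in the SAP requires the Low before a High, restarts a course at Low, or cancels the Highs when the Low is missed. The literal result is a High without its Low.

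**Step 2: calendar.** Trial day = 7 × (week − 1) + day. I assume that day 1 is a Monday and that nothing is delayed. Then week 3 day 1 is day 15, week 3 day 5 is day 19, and week 8 day 1 is day 50. A course is three days, each at least 2 days after the one before, all within 7 days.

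With weekday dosing, the last loading dose falls on day 5 to 12, the second maintenance dose (the first High) on day 52 to 59, and the last schedule 4 concurrent dose on day 19.

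| Gap before the maintenance High if its Low is forfeited | Schedule 3 | Schedule 4 |
|---|---|---|
| Shortest, weekday dosing | 52 − 12 = 40 days | 52 − 19 = 33 days |
| Longest, weekday dosing | 59 − 5 = 54 days | 59 − 19 = 40 days |
| Dosing on any day | 52 − 14 = 38 to 61 − 5 = 56 days | 33 to 61 − 19 = 42 days |

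If the day 19 dose moves to the next radiotherapy day (day 22) under section 8.3, the schedule 4 minimum is 52 − 22 = 30 days.

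As planned, the longest gap before any High is 4 days in schedule 3 (within a 7-day course) and 15 − 5 = 10 days in schedule 4 (last loading dose to week 3 day 1).

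**Step 3: loading course.** No dose precedes it. If its Low is forfeited, the High is the first exposure.

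**Step 4: how often a later start still fits.** A full weekday maintenance course can start on day 50, 51, 52, 53, 54 or 57. From five of these six dates there is a later start that fits all three doses. Only a Low planned for day 57 has none, and two doses still fit then (for example days 58 and 60). Weeks 1-2 are the same calendar 49 days earlier: starts on days 1 to 5 and 8, again five of six.

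**Step 5: what enforcing the order costs in dose and weight.** The planned total D (in 10^12 vp) is 1+3+3+1+3+3 = 14 in schedule 3 and 14+3+3 = 20 in schedule 4. The SAP section 6.2.1 weight for a patient without a DLT, followed for the whole window, is ½(1 + v/D), where v is the dose received.

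| Dosing days left in the maintenance course | Course dose, literal 8.5 | Course dose, order rule | Schedule 3 weight | Schedule 4 weight |
|---|---|---|---|---|
| Two | 3+3 = 6 | 1+3 = 4 | 13/14 gives 0.96; 11/14 gives 0.89 | 19/20 gives 0.98; 17/20 gives 0.93 |
| One | 3 | 1 | 10/14 gives 0.86; 8/14 gives 0.79 | 16/20 gives 0.90; 14/20 gives 0.85 |

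In each weight cell the literal rule comes first and the order rule second. The differences arise only if the formula is applied to patients who complete the window. Protocol section 17.1 and SAP section 6.2.1 also say in words that such patients contribute full information. On that text the weight is 1 either way.

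**The case against.** The best reply is that section 8.5 should not be read apart from section 8.2. Section 8.2 numbers the doses in each course, and a course that opens with 3 × 10^12 vp is not the pattern it describes. The dosing days are flexible, so a Low not given on its intended day is naturally seen as moved, not missed. This is plausible and makes the situation uncommon on the calendar. It does not settle the matter, because section 8.5 never says when a moved dose becomes a missed one. The protocol does write a delay rule where it wants one: if capecitabine was taken on a dosing day, "administration of enadenotucirev should be delayed to the next day of radiotherapy". That rule is tied to radiotherapy days, so it covers neither weeks 1-2 nor weeks 8-9.

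The second reply concerns harm, and most of it stands. Section 1.2 gives 3 × 10^12 vp as the maximum tolerated dose from the completed studies. Section 8.3 requires antipyretic and steroid prophylaxis and hydration at every dose. A patient who reaches weeks 8-9 with no earlier missed dose has already had High doses without a DLT. Schedule 4 itself gives a High on week 3 day 1 without a new Low, though at most 10 days after the last loading dose. In the loading course, the longer 6-hour monitoring of section 5.4 would apply.

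A reader might infer that the rule raises the DLT rate in schedules 3 and 4, or that patients who miss a Low will in fact be given a High. The documents support neither. They report no DLT rate for a High without its Low. The adverse event table in section 9.2 compares dose levels, not Highs with and without a lead-in. The few days in section 1.2 say when attenuation is seen; they set no limit after which a High is unsafe. The gaps in days measure time, not risk.

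**Conclusion.** The point holds as a minor patient-safety improvement. The wording of section 8.5, followed literally, can drop the Low dose that section 1.2 relies on, in the loading as well as the maintenance course of schedules 3 and 4. The gap lengths rest on the nominal calendar with weekday dosing; dosing on any day widens them only a little. How often it would happen cannot be estimated, because the documents give no frequency of missed doses. No endpoint, dose-decision rule or main analysis is affected.

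**What to change.** Add one paragraph to section 8.5 at the next amendment:

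> In any Low-High-High course (loading or maintenance), no 3 × 10^12 vp dose is given until the 1 × 10^12 vp dose of that course has been given. If the first date is missed for a reason other than toxicity, the course starts later with 1 × 10^12 vp and the order continues; doses that no longer fit before CRT starts (loading) or within weeks 8-9 (maintenance) are omitted. This is not a dose modification. The same order applies if dosing resumes after a toxicity interruption, and the rule that two consecutive doses missed for enadenotucirev toxicity are a DLT is unchanged.

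The schedule 4 concurrent doses in week 3 and the analysis by assigned schedule stay as they are. No patients or visits are added, and nothing is lost when a full later course fits. Otherwise the patient receives 2 × 10^12 vp less in that course than under the literal rule. The sponsor has to accept that trade. The small loss of weight shown above follows only if the SAP formula is applied to patients who complete the window.
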